### 3.2 Overall Design

This is a Phase 2, multi-center, open-label, proof of concept study designed to assess the effect of setmelanotide on weight loss on a population affected by HO. Approximately 15 patients aged 6 to 40 years, inclusive, are planned to be enrolled across approximately 3-5 clinical sites in the United States.

Patients will first enter the Screening Period, during which they will be assessed for eligibility and complete all screening procedures as described in the Schedule of Activities (SoA) ([Section 16.1](#)). Individuals who do not meet the criteria for participation in this study (screen failure) may be eligible for rescreening at a later date, depending on the reason for the initial screen failure and provided enrollment is still open. If a patient is approved for rescreening by the Sponsor, the rescreened patient should be assigned the same Screening number as for the initial screening. Up to 3 screenings per patient are allowed (2 screening failures).

Patients who are determined to be eligible, based on screening assessments, will return to the clinic for the Baseline Visit (Visit 2) and receive their first setmelanotide dose. Patients will return to the study center for Visits 3, 4, and 5 (Weeks 4, 8, and 12, respectively), with each of these visits conducted approximately 4 weeks apart. All patients will return to the study center at Week 16 (Visit 6) and receive the last setmelanotide injection. After completion of Visit 6, participation in the current study will then conclude in one of the following 2 ways:

1. Patients meeting the primary endpoint meeting may be eligible to be enrolled in a separate extension study, Rhythm Study RM-493-022, under which auspices the patient will continue to receive setmelanotide.
2. Patients who do not meet the primary endpoint or elect not to continue setmelanotide are to discontinue setmelanotide at Visit 6 and return for an End-of-Study Visit (Visit 7) 4 weeks thereafter for a final safety review under the auspices of the current study.

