### 3.4 Determination of Sample Size

The objective of this study is to evaluate safety and preliminary efficacy on weight loss in patients with HO. The primary endpoint is the proportion of patients who achieve at least 5% BMI reduction from baseline at ~16 weeks of treatment with setmelanotide. Given the exploratory nature of the study, the sample size is primarily driven by clinical considerations, with the considerations of statistical testing. It is planned to enroll ~5-10 patients aged >12 years, and up to 10 patients between 6 and 12 years. With 10 patients aged >12 years and up to 10 patients aged 6 to 12 years, at 1-sided 0.05 significance level, the study provides ~90% power to reject the null hypothesis that the true response rate is less than historical control rate of 5%, assuming a 40% target response rate in setmelanotide.

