## 9.1 Primary Efficacy Endpoint

The primary endpoint is defined as the proportion of patients who achieve at least 5% BMI reduction from baseline, at ~16 weeks of treatment with setmelanotide. BMI will be calculated using patient's weight and height assessments, using the following formula:

$$BMI = \frac{kg}{m^2}$$

If needed, weight and height will first be converted into kilograms and meters, respectively. Given that body weight is collected in triplicates at each visit, weight (kg) will first be aggregated into one averaged weight per visit. Visits will then be compared against the analysis visit window (described in [Section 4.2](#)) to select the Week 16 averaged weight prior to calculating BMI and change in BMI. Patients who are  $\geq 18$  years of age will only have height measurement done at screening; the averaged triplicate

screening height will be used for the height component of the BMI calculation at each visit. Patients who are < 18 years of age will have their height measured in triplicates at most study visits. As with body weight, height will first be aggregated into one averaged height per visit and compared against the analysis visit window to select the Week 16 averaged height. Regardless of reason, if height is missing for an analysis visit, then height will be imputed using last observation carried forward (LOCF). Change ( $\Delta$ ) in BMI (%) from baseline at 16 weeks of treatment will be calculated as follows:

$$\Delta \text{ BMI } (\%) = \left( \frac{\text{Week 16 BMI} - \text{Baseline BMI}}{\text{Baseline BMI}} \right) * 100$$

An indicator variable will then be created to identify patients that have a decrease in BMI from baseline to Week 16 of 5% or more, allowing for the analysis of proportion of patients who achieve at least 5% BMI reduction.

The primary endpoint will be assessed using an exact binomial test at a 1-sided 0.05 significant level, compared to the null hypothesis proportion of 0.05 (which comes from a historical control rate of 5%). The number of and the binomial proportion of patients who achieve at least 5% BMI reduction from baseline at 16 weeks, the corresponding 2-sided 90% CI, and one-sided binomial test p-value will be presented. The Clopper-Pearson method will be used to calculate the CI. A scatter plot figure will also be created plotting each patient's percent BMI reduction from baseline to Week 16.

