### **11 Statistical/Analytical Issues**

#### **11.1 Handling of Missing Data**

In general, the number of patients with missing values will be summarized and reported as appropriate in all outputs. Calculations for all questionnaires will follow the methods specified in the specific sections of this SAP for the handling of the data.

For primary and key secondary analyses, missing data for Week 16 body weight and BMI will be imputed using LOCF. With the LOCF imputation method, if a patient is missing their Week 16 assessment, their last non-missing assessment will be used. Given that BMI will be calculated using patient's weight and height measurements, if height is missing for any analysis visit, height will be imputed using LOCF.

The primary analysis may be repeated using multiple imputation (MI) as a sensitivity analysis as needed. If performed, MI methods are specified in [Section 16.5](#).

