## 16.5 Multiple Imputation Methods

As stated in [Section 11.1](#), the MI procedure may be performed as needed as a sensitivity analysis. If performed, the following methods will be used:

Missing data for Week 16 will be imputed using MI under the Missing at Random (MAR) assumption. Change from baseline in BMI will be derived from the corresponding imputed values. The following steps will be followed to create the imputations:

- 1.1. Regardless of the actual pattern of missing data, the Markov Chain Monte Carlo (MCMC) method of the SAS PROC MI procedure will first be used to make it monotone. The single chain method will be used. The minimum values for imputed variables will be set to 0, in order to force PROC MI to redraw another value for imputation when an intended imputed value is less than the 0. Imputed values will be rounded to the nearest integer. The seed number will be set to 112595 and 5 imputations will be created.
- 1.2. The SAS PROC MI will be used for imputing missing values of data with monotone missing pattern. One imputation will be made using each of the 5 MCMC-imputed datasets. A linear regression model will be used with covariates for non-missing BMI from earlier scheduled time points including baseline as well as age. The minimum values for imputed variables will be set to 0, in order to force PROC MI to redraw another value for imputation when an intended imputed value is less than the 0. Imputed values will be rounded to the nearest integer. Change from baseline in BMI will be derived from the corresponding imputed values.
- 1.3. If the monotone pattern does not converge, the imputations will be created with an arbitrary missing data pattern. The seed number will still be set to 112595 and 5 imputed datasets will be created by fully conditional specification (FCS). One imputation will be made using each of the 5 imputed datasets. A linear regression model will be used with covariates for non-missing data from earlier scheduled time points including baseline as well as age. The minimum values for imputed variables will be set to 0, in order to force PROC MI to redraw another value for imputation when an intended imputed value is less than the 0. Imputed values will be rounded to the nearest integer. Change from baseline will be derived from the corresponding imputed values.
2. The imputed datasets will be analyzed as specified in the respective Section 9.

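### The optional multiple-imputation sensitivity analysis uses only 5 imputations, which leaves avoidable simulation noise in the pooled responder rate

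*SAP*

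**What the plan says.** SAP 16.5 describes a two-stage imputation. Step 1.1 makes the missing pattern monotone by MCMC: "The seed number will be set to 112595 and 5 imputations will be created". Step 1.2 then draws one regression imputation from each of those 5 datasets. Step 1.3, the fully conditional fallback, keeps the same seed and again 5 datasets. Step 3.1 pools the binary results into a proportion, a 95% confidence interval and a p-value with PROC MIANALYZE. No step justifies 5, sets a Monte Carlo error target or asks for a check under other seeds.

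The analysis is optional. SAP 11.1 says: "The primary analysis may be repeated using multiple imputation (MI) as a sensitivity analysis as needed". The main handling of missing values is different: "For primary and key secondary analyses, missing data for Week 16 body weight and BMI will be imputed using LOCF". The test of the primary endpoint is also separate from MI. SAP 9.1 says: "The primary endpoint will be assessed using an exact binomial test at a 1-sided 0.05 significant level, compared to the null hypothesis proportion of 0.05".

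On trial size, SAP 3.2 says: "Approximately 15 patients aged 6 to 40 years, inclusive, are planned to be enrolled".

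**The concern.** The imputed quantity is Week 16 BMI, but what is reported is a yes/no indicator of at least 5% reduction. Each imputed patient therefore enters a given dataset as 0 or 1, and one patient in 15 is a large step. Averaging 5 such datasets gives a coarse estimate that still depends on the random draw. Fixing the seed makes the run repeatable. It does not bring the answer closer to the value that many imputations would give.

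A robustness check should not add simulation error that can be removed for nothing. MI is also the only alternative imputation method that the SAP offers against LOCF. The other listed sensitivity analysis is a per-protocol repeat, and SAP Table 2 excludes patients without a Visit 6 weight from that set. If the MI analysis is run, it will be because some Week 16 values are missing and LOCF is in question, so its result should be stable.

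**Working it through.** **Plan's own figure.** The plan states no Monte Carlo error, so there is none to reproduce. Its approximate 90% power figure (SAP 3.4) does not enter this point. For the record, the exact test gives 83.3% at N = 10, 97.3% at N = 15 and 98.4% at N = 20, which is a separate matter.

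**Inputs.**
- N = 15 (SAP 3.2); m = 5 imputations (SAP 16.5); null rate 0.05, one-sided 0.05 (SAP 9.1).
- k, the number of patients without a Week 16 BMI: not given. Assumed 1 to 4.
- q, the chance that an imputed value is a responder: not given. Assumed 0.4, the planning rate in SAP 3.4 ("assuming a 40% target response rate in setmelanotide").

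**Step 1: granularity.** One responder is 1/15 = 6.7 points. The mean of 5 datasets moves in steps of 6.7/5 = 1.33 points.

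**Step 2: noise in the pooled rate.** Treating imputed statuses as independent, the seed-to-seed SD is √(k·q·(1−q)) / (N·√m). For k = 1, m = 5: √0.24 / (15 × 2.236) = 0.490/33.5 = 1.5 points.

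| Missing (k) | m = 5 | m = 50 | m = 100 |
|---|---|---|---|
| 0 | 0 | 0 | 0 |
| 1 | 1.5 | 0.5 | 0.3 |
| 2 | 2.1 | 0.7 | 0.5 |
| 3 | 2.5 | 0.8 | 0.6 |
| 4 | 2.9 | 0.9 | 0.7 |

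(percentage points). With q from 0.2 to 0.5, the m = 5 column spans 1.2 to 3.0. Going from 5 to 100 divides the SD by √20, about 4.5.

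Example: 4 observed responders and 2 missing. The central 95% of seeds give pooled rates of 28.0% to 36.0% at m = 5, and about 31.1% to 33.0% at m = 100.

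**Step 3: check with an actual regression imputation.** The formula uses one q for all missing patients. A simulation with regression imputation of BMI (assumed mean 37, SD 6, SD of percentage change 7) gave an average SD of about 0.8 to 2.2 points at m = 5. At a true 40% response rate it fell from 1.0–2.2 points at m = 5 to 0.3–0.7 at m = 50, and integer rounding made little difference to the SD. The formula is therefore somewhat on the high side, but of the right order.

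**Step 4: can the sensitivity p-value change?** Step 3.1 does not say how exact binomial results enter PROC MIANALYZE. Two readings:

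- *Wald pooling by Rubin's rules*: T = W + (1 + 1/m)·B and t = (pooled rate − 0.05)/√T, where W and B are the within- and between-imputation variances. With 3 observed responders, the share of seeds with one-sided p < 0.05 at m = 5 is about 9%, 41%, 67% and 81% for 1, 2, 3 and 4 missing. At m = 100 it is 0%, 90%, 100% and 100%. With 4 observed responders at least 99% of seeds agree. With 5 or more, all do.
- *Exact test within each dataset*: at N = 15, P(X ≥ 3) = 0.036 and P(X ≥ 2) = 0.171 under a 5% rate, so 3 responders suffice. With 3 observed responders every imputed dataset rejects, whatever the seed. With 2, a dataset rejects only if at least one imputed patient responds, with probability 1 − 0.6^k = 0.40, 0.64, 0.78 and 0.87 for k = 1 to 4, so the draw still matters there.

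The two readings differ because the Wald statistic at 3/15 is 0.15/√(0.2 × 0.8/15) = 1.45, short of 1.645, and first passes at 4/15 (1.90). Much of the instability at 3 responders thus comes from replacing the exact test by Wald pooling, not from m.

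**The case against.** The strongest reply is that nothing of consequence rests on this analysis. It may never be run, it is a sensitivity analysis, and no go/no-go rule refers to its p-value. A reader might infer that the trial's conclusion depends on the random seed. The documents do not support that, because the primary result comes from LOCF and the exact binomial test, neither of which involves a random draw. A reader might also infer that the seed could be chosen to suit. It cannot, because it is fixed in advance. These replies stand.

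The noise is also small beside sampling error. At a 40% rate the standard error is √(0.4 × 0.6/15) = 12.6 points, and the 90% Clopper-Pearson interval for 6/15 is 19% to 64%. Adding 1.5 to 2.9 points in quadrature raises the standard error by only 0.7% to 2.6%, and Rubin's factor (1 + 1/m) already allows for a finite m. This stands as to size. It does not make the noise useful: sampling error cannot be removed at the analysis stage, and this can.

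Finally, the amount missing is unknown, and the protocol's section on discontinuation and withdrawal describes active retention support. If every patient has a Week 16 BMI, the effect is nil. That stands too, and in that case the change costs nothing.

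**Conclusion.** The point holds as a minor one. Five imputations leave a seed-to-seed SD of about 1.5 to 2.9 points in the pooled responder rate, against 0.3 to 0.7 with 100. This assumes 15 patients, 1 to 4 missing and a 40% imputed response chance; only the first comes from the documents as a planned figure for the trial's size. The primary analysis is untouched.

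The sensitivity p-value can change with the seed only near the boundary, at roughly 2 to 4 observed responders depending on the number missing and the pooling. No single figure for how often that happens can be taken from the documents. Under Wald pooling the regression simulation found a seed-dependent verdict in 0 to 24% of trials at a true 40% rate, a range that describes its inputs more than this trial. This is a free improvement in precision, and nothing stronger should be claimed.

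**What to change.** In SAP 16.5, replace 5 by 100 wherever the number of imputations or imputed datasets appears in steps 1.1, 1.2 and 1.3. The seed can stay. The cost is one number in the SAP and a few seconds of run time; design, data collection and primary analysis do not change.

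Two neighbouring issues need their own correction and are not cured by more imputations. First, imputed values are rounded to whole numbers, although at an assumed BMI of 37 a 5% change is only 1.85 units. Second, step 3.1 does not say how exact binomial results are pooled, and it reports a 95% interval where the primary analysis uses a two-sided 90% Clopper-Pearson interval.
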